2.2.12 Safety Pharmacology

In an extensive survey of diverse enzyme functions, including kinases, receptors and ion channels, no significant interactions (inhibition $> 50\%$ at 10 μM) were noted, with the exception of a mild to moderate inhibition (IC_{50} 1.3 μM) of the enzyme 5-lipoxygenase.

ACY-1215 has no activity against the human ether-à-go-go related gene (hERG) channel in vitro at 10 μM and showed 18% inhibition at the solubility limit of ~62 μM , i.e. 12 – 60 fold higher than the expected efficacious concentration.

In beagle studies, dose levels of 10, 30, and 60 mg/kg of ACY-1215 produced a moderate and transient rise in heart rate (19 – 24 bpm) with a modest decrease in systolic pressure (5 - 15 mm Hg) observed at 0.5 - 11 hours post-dose for all 3 dose levels. One beagle in the highest dose group (60 mg/kg) with the highest exposure and maximum concentrations (C_{max}) levels of ACY-1215 exhibited a QTcR prolongation 15 – 24 hours post-dose, with a maximal excursion of 32 ms (13.4%), and an average excursion for the time period of 20 ms (8.3%) compared to pre-dose values. Plasma levels of ACY-1215 during this period were at least 100-fold below the concentration of ~62 μM , where a minimal 18% inhibition of the hERG channel was observed.

ACY-1215 did not elicit any changes in respiratory or central nervous system function.

2.2.13 Pre-Clinical Pharmacokinetic Studies

ACY-1215 is rapidly absorbed (time to maximum concentration [T_{max}] ≤ 1 hour) following oral administration in the mouse, rat, and dog, with an oral bioavailability of 11% to 19% in rodents and approximately 45% in dogs. Allometric scaling between species suggests the pharmacokinetic profile of ACY-1215 in humans will be similar to that observed in dogs. Pharmacodynamic studies in mice with ACY-1215 demonstrated a reversible increase in levels of acetylated α -tubulin, a biomarker of HDAC6 inhibition, in peripheral blood mononuclear cells (PBMCs). ACY-1215 is classified as moderately permeable and is stable in human liver microsomes (half-life [$\text{t}_{1/2}$] > 45 minutes).

Two major metabolites were identified in human S9 liver and intestinal microsomes, which were also present in plasma samples from toxicological studies rat and dog. ACY-1215 and the

2 major metabolites have minimal potential to cause drug-drug interactions through inhibition or induction of CYP450 enzymes.

2.2.14 Pre-Clinical Toxicology

ACY-1215 administered by the oral route has been extensively studied in toxicological studies including pivotal 28 Day repeat-dose studies in rats and dogs. Exposure in the dog for ACY-1215 was considerably higher than in rats by 21- to 31-fold due to higher bioavailability in the dog. Severe toxicity has not been observed at any dose level after administration of ACY-1215 in rats and dogs.

In the rat, a 28 Day repeat-dose study, which included a neurobehavioral functional observation battery and motor assessment, no significant findings were observed after administration of ACY-1215 at dose levels of 30, 60, and 120 mg/kg. The no observed adverse effect level (NOAEL) in rat for the nominal dose is considered to be 120 mg/kg. The NOAEL in the rat for the exposure level is considered to be 30 mg/kg due to the slight increase in exposure with increasing dose on Day 28.

Significant toxicological findings were restricted to the pivotal dog 28 Day repeat-dose study and were generally minimal to mild in nature. The findings were partially or fully recoverable following a 14-day recovery phase. Slight decreases in body weight and minimal to mild decreases in red blood cell mass was observed at all 3 dose levels of 30, 60, and 120 mg/kg, while decreases in white blood cells, lymphocytes, and monocytes were observed in males. The decreased red blood cell mass may reflect decreased hematopoiesis and/or increased turnover of red blood cells suggested by minimal to slight pigment deposition in the liver of some dogs. Marginal, non-adverse, though statistically significant from the control group, clinical chemistry changes were noted in both genders in all dose groups, including a decrease in hepatic enzyme activities (alanine transaminase, alkaline phosphatase, and gamma-glutamyl transferase) and increases in triglyceride (males), total bilirubin (high dose male), albumin and total protein. Administration ACY-1215 at all dose levels was associated with decreased thyroid/parathyroid weights by 27-49% (males) and decreased thymus gland weights by 59-65% (females). There were no histological correlates for the organ effects. A NOAEL in the dog was not established due to the hematological findings and slight but statistically significant body weight effects, which were present at all dose levels.

The mutagenic potential for ACY-1215 appears to be low. ACY-1215 did not exhibit mutagenicity in either the Ames test or Chinese hamster ovary (CHO) micronucleus test. ACY-1215 did not display a mutagenic potential in the mouse lymphoma mutation assay, except with metabolic activation at concentrations 46- to 460-fold above the therapeutic range in cellular assays with MM cells.

Detailed descriptions of findings from nonclinical studies of ACY-1215 are summarized in the Investigator's Brochure.

2.2.15 Clinical Data

ACY-1215 monotherapy was administered at doses to 360 mg without any observed dose limiting toxicities.. Across all dose levels, the most common treatment-emergent adverse events reported among 15 patients treated with ACY-1215 monotherapy were elevated creatinine (5 patients; 33%), anemia, fatigue, hypercalcemia, and upper respiratory infection (4 patients each;

27%), and cough, diarrhea, dizziness, and low white blood cell count (WBC) (3 patients each; 20%). Of these events, diarrhea and low WBC only occurred at doses ≥ 160 mg. Grade 3 adverse events that were considered by the investigator to be at least possibly related to study drug occurred at doses of 160 mg and 360 mg, and included anemia and decreased WBC and absolute neutrophil count; no Grade 4 events were reported.

Pharmacokinetic analysis of ACY-1215 monotherapy revealed measurable levels of ACY-1215 in all patients, with maximum plasma concentration (C_{max}) levels ranging from 85 ± 39 to 503 ± 195 ng/mL (0.2 to 1.2 μ M) and area under the concentration curve from time 0 to the last time point of quantifiable drug concentration (AUC_{last}) values ranged from 170 ± 61 ng \cdot h/mL to 1093 ± 357 ng \cdot h/mL at dose levels of 40 to 360 mg.[1] Maximal plasma (C_{max}) and exposure (AUC) levels were observed in patients treated at 160 mg (C_{max} 626 ± 150 ng/mL, and AUC_{last} 1074 ± 439 ng \cdot h/mL) and 240 mg (C_{max} 719 ± 329 ng/mL, and AUC_{last} 1231 ± 430 ng \cdot h/mL), suggesting an exposure plateau was reached at dose levels ≥ 160 mg.[1]

The drug was rapidly absorbed (T_{max} ~1 hour) from the gastrointestinal tract. The apparent elimination half-life was ~3 hours. By 24 hours post-dose, drug levels ranged from ~1 ng/mL to below the lower limit of quantification (0.5 ng/mL). There was no accumulation of drug observed over multiple days of administration [28] Overall drug exposure was similar for all doses greater than 160 mg..

Pharmacodynamic analyses in peripheral blood mononuclear cells (PBMCs) revealed acetylation of tubulin at starting at the 40mg dose and that this peaked to a 2-fold increase in acetylated tubulin, the pharmacological marker of HDAC6 inhibition, in all patients at doses of ≥ 160 mg. At doses higher than 160 mg, a modest increase in acetylated histones was demonstrated with ACY-1215 monotherapy.

Taken together, the data show that exposures observed at ACY-1215 doses ≥ 160 mg achieve the target change in pharmacodynamic markers such as acetylated tubulin, while sparing acetylation of H3 (an off-target effect), and attain drug levels in the range where efficacy was observed in nonclinical studies[28] These drug levels plateaued at 160 mg so further increases in dosing did not lead to increased in drug exposure.

Further information about ACY-1215 can be found in the investigator brochure.

2.3 Rationale for Phase Ib Study Design

Given that the experience of ACY-1215 monotherapy is limited and restricted to patients with multiple myeloma, a Phase Ib study will be performed exclusively in patients with lymphoma. In addition, in the previous Phase I myeloma experience the dosing schedule was on days 1-5, 8-12 of a 21day cycle. In the prior Phase I study, DLTs were never reached at the dose of 360 mg daily, although pharmacodynamics endpoints were met and the maximum plasma concentrations plateaued at 160 mg daily dosing. This current study is designed to evaluate two dosing schedules of the recommended dose (see above Section 2.2.14) for safety and tolerability while maximizing intensity of exposure to the study drug. Given the half-life of elimination ranges from 3-4 hours, dosing every 12 hours will be explored. Patients of all lymphoma subtypes will be enrolled in order to broaden the experience with ACY-1215 monotherapy. Three patients will be sequentially enrolled in one of two cohorts: Arm A and then after a safety assessment has occurred, Arm B for a total of six patients (3 in each arm). If $\leq 33\%$ of patients ($N\leq 1$) experiences a dose limiting toxicity (DLT) in a cohort, the cohort will be expanded to 6 patients

(3+3). If there are \leq 33% (N \leq 2 DLTs), the cohort will be further expanded to a total of 10 patients (3+3+4). The total number of patients for both Arms A and B with full expansions will total 20. If more than 1/3 or 2/6 patients experience a DLT, there will be no expansion. Safety data obtained from this Phase Ib will be analyzed by the sponsor and collaborating investigators to recommend a Phase II dose and schedule.

3. PATIENT SELECTION

3.1 Inclusion Criteria for Lymphoma

Patients meeting all of the following criteria will be considered eligible for enrollment in the study:

1. Patients must have histologically confirmed relapsed or refractory non-Hodgkin's lymphoma or Hodgkin's lymphoma (WHO criteria), for which they are unwilling or unable to undergo an autologous stem cell transplant. Patients may have relapsed after prior stem cell transplant.
2. Must have received first line chemotherapy. No upper limit to number of prior therapies.
3. Patients must have measurable disease.
4. Patients must be age \geq 18.
5. Patient has a Karnofsky Performance Status score of \geq 70 or ECOG \leq 2
6. The patient or the patient's legal representative is able to understand the risks of the study and provide signed informed consent and authorization to use protected health information (in accordance with national and local privacy regulations).
7. Patient has adequate bone marrow reserve, as evidenced by:
 - Absolute neutrophil count (ANC) of \geq 1.0 \times 10⁹/L.
 - Platelet count of \geq 50 \times 10⁹/L.
8. Patient has adequate renal function, as evidenced by a CR within the institutional limits of normal or a calculated creatinine clearance of \geq 30 mL/min according to the Cockcroft-Gault equation.
9. Patient has adequate hepatic function, as evidenced by serum bilirubin values $<$ 2.0 mg/dL and serum alanine transaminase (ALT) and/or aspartate transaminase (AST) values $<$ 3 \times the upper limit of normal (ULN) of the local laboratory reference range. (Patients with isolated elevations in alkaline phosphatase [ALP] $<$ 5 \times ULN in the presence of bony disease are not excluded from participating in the study.)
10. Females of childbearing potential must have a negative urine or serum pregnancy test within 7 days of (C1D1) and have adequate contraception. (A female is considered to be NOT of childbearing potential if she has undergone bilateral oophorectomy or if she has been menopausal without a menstrual period for 12 consecutive months.)

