5.1.3 Required Blood Parameters and Other Investigations Prior to Each Treatment

Before the start of each treatment cycle, patients should be reassessed and the following criteria must be fulfilled:

- Karnofsky Score \geq 70 or ECOG Performance Status \leq 2

- ANC > 1000/dL
- Platelet count \geq 50,000
- Serum creatinine concentration $\leq 2.0 \times$ ULN or \leq baseline, or creatinine clearance >30 mL/min
- AST (SGOT) and ALT (SGPT) $\leq 3.0 \times$ ULN or $\leq 3.0 \times$ ULN in presence of demonstrable liver metastases
- Bilirubin concentration $\leq 2.0 \times$ ULN
- Recovery of any drug-related non-hematological toxicity to Grade 1 or less, unless otherwise indicated

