6. DOSING DELAYS/DOSE MODIFICATIONS

6.1 Dose Delays

- Study drugs will be held until adverse event returns to \leq Grade 2.
- If interruption lasts for more than 14 days, study treatment will be discontinued.
- In patients who miss $>10\%$ of planned dose in the Phase II, but not the Phase Ib, data will be censored for response, but not for toxicity, and patients will be replaced for adequate response assessment.

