6.3.1 ACY-1215 Dose Modifications

In general, if study drug has been held and the toxicity does not resolve, as defined above, then drug must be discontinued. Note: Dose reductions should not be performed for alopecia or for nausea or vomiting that was not treated with aggressive anti-emetic support. Dose modifications are described in detail in the table below.

Table 2: Dose Modifications for ACY1215

Dose Modifications for ACY1215	
CTCAE Grade or Abnormal Value	1) ACY1215
Thrombocytopenia	
Grade 1 ($75 \times 10^9/L - < LLN$) Grade 2 ($50 - < 75 \times 10^9/L$)	Maintain dose level 2) Maintain dose level
Grade 3 or 4 thrombocytopenia: OR Thrombocytopenia that requires platelet transfusion or recurrent Grade 3 or 4 thrombocytopenia	Hold subsequent doses of therapy until thrombocytopenia returns to \leq Grade 2 or baseline and continue at full dose Hold subsequent doses of therapy until thrombocytopenia returns to \leq Grade 2 or baseline and permanently reduce dose of ACY1215 to 75% of dose. If the same toxicity recurs despite dose reduction, reduce by an additional 25%.
Neutropenia (ANC)	
3) Grade 1 ($1.5 \times 10^9/L - < LLN$) 4) Grade 2 ($1.0 - < 1.5 \times 10^9/L$)	5) Maintain dose level 6) Maintain dose level
7) Grade 3 and 4 neutropenia:	8) Hold subsequent doses of therapy until specific cytopenia returns to \leq Grade 1 or baseline and continue at full dose
9) Febrile Neutropenia	
Febrile ($\geq 38.5^\circ C$) Grade 4 neutropenia or recurrent Grade 3 or 4 neutropenia:	10) Hold subsequent doses of therapy until neutropenia returns to \leq Grade 1 or baseline and permanently reduce dose of ACY1215 to 75% of dose. If the same toxicity recurs despite dose reduction, reduce by an additional 25%.
11) All Other Non-Hematologic Drug Toxicities (not mentioned in previous tables)	
Grade 1 or 2:	12) Maintain dose level
Grade 3	Hold treatment with ACY1215 until toxicity returns to \leq Grade 1 or baseline, then restart therapy at full dose. If Grade 3 toxicity recurs, reduce dose of by 25%. This is a permanent dose reduction.
Grade 4	Grade 4 toxicity: Hold treatment with ACY1215 until toxicity returns to \leq Grade 1 or baseline, and then restart therapy at 25% dose reduction. This is a permanent dose reduction

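### The mandatory pre-cycle neutrophil limit carries the wrong unit (per dL), which puts it 100,000 times below the entry limit and leaves the check with almost no effect

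*Combined protocol and SAP*

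**What the plan says.** Four parts of the protocol set neutrophil rules or bear on them.

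- **Entry (Section 3.1, item 7).** The criterion is an "Absolute neutrophil count (ANC) of" 1.0 × 10^9/L or more. The platelet limit is 50 × 10^9/L or more.
- **Start of each cycle (Section 5.1.3, Required Blood Parameters and Other Investigations Prior to Each Treatment).** The list is mandatory: "Before the start of each treatment cycle, patients should be reassessed and the following criteria must be fulfilled". It asks for an ANC above 1000 per dL and platelets of at least 50,000, the latter with no unit. Its only recovery line concerns other toxicities: "Recovery of any drug-related non-hematological toxicity to Grade 1 or less".
- **Dose holds (Section 6.1 and Table 2 in Section 6.3.1).** Table 2 works in units of 10^9/L and puts Grade 2 neutropenia at 1.0 to below 1.5. For "Grade 3 and 4 neutropenia" the instruction is "Hold subsequent doses of therapy until specific cytopenia returns to" Grade 1 or lower, or baseline. Section 6.1 has a general rule, "Study drugs will be held until adverse event returns to" Grade 2 or lower, and ends treatment after an interruption of more than 14 days.
- **Attribution (Section 6.3).** Where a toxicity is considered unrelated to the drug, no modification of that drug is required.

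**The concern.** The pre-cycle list decides whether a patient may begin another cycle, and its ANC line is the only item on that list that deals with neutrophils. If the number and unit are taken literally, the line cannot do its job, and nothing else in the same list replaces it. No other text in the protocol corrects the unit.

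A site then has different neutrophil levels to choose from on Day 1 of a cycle: one that is nearly zero in Section 5.1.3, Grade 2 or better in Section 6.1, and Grade 1 or baseline in Table 2. The pre-cycle list applies whatever the cause of the low count, whereas Section 6.3 makes modification depend on attribution. A working pre-cycle limit would therefore be the clearest floor for a patient whose neutropenia is put down to the lymphoma or another cause. The rule governs up to 60 Phase II patients, with no cap on the number of cycles.

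**Working it through.** **Inputs.** Pre-cycle limit: 1000 per dL (Section 5.1.3). Entry limit: 1.0 × 10^9/L (Section 3.1, item 7). Lower edge of Grade 2 neutropenia: 1.0 × 10^9/L (Table 2), so Grades 3 and 4 lie below 1.0. Conversions: 1 L = 10 dL = 10^6 µL.

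**Step 1. Put both limits on one scale.**
- Pre-cycle: 1000/dL × 10 dL/L = 10,000/L = 0.00001 × 10^9/L = 0.01 per µL.
- Entry: 1.0 × 10^9/L = 1000 per µL = 100,000,000 per dL.
- Ratio: 1,000,000,000 / 10,000 = 100,000.

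**Step 2. See who fails each version of the check.**

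| ANC (× 10^9/L) | Same count per dL | Above 1000/dL? | Above 1000/µL? |
|---|---|---|---|
| 1.5 | 150,000,000 | passes | passes |
| 1.0 | 100,000,000 | passes | fails |
| 0.5 | 50,000,000 | passes | fails |
| 0.1 | 10,000,000 | passes | fails |
| 0.01 | 1,000,000 | passes | fails |
| 0.0001 | 10,000 | passes | fails |
| 0.00001 | 1,000 | fails | fails |
| 0 | 0 | fails | fails |

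The literal limit excludes only counts at or below 0.01 per µL, in practice a reported zero. The protocol does not print the Grade 4 cut-off, but the result does not depend on it: for any cut-off above 0.00001 × 10^9/L, Grade 4 patients with counts between the two values pass.

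**Step 3. Find the intended unit.** A limit of 1000 equals 1.0 × 10^9/L per µL, 0.001 per mL, 0.00001 per dL and 0.000001 per L. Only per µL (equivalently per mm³) reproduces the entry limit. The platelet line agrees: 50,000/µL × 10^6 µL/L = 50 × 10^9/L, which is the entry platelet limit.

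**Step 4. Ask what else stops dosing.** Drug-related Grade 3 or 4 neutropenia is held under Table 2, and Day 1 of a new cycle is a subsequent dose. If the neutropenia is judged unrelated, Section 6.3 requires no modification. Section 6.1 states no attribution condition, so a site could read it either way.

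**Step 5. Check the link to dose-limiting toxicity.** Section 5.1.4 counts toxicity that delays cycle 2, up to 7 days after cycle 1 ends. It does not say that the delay must come from the pre-cycle list. A Table 2 hold also delays cycle 2, and its recovery level (Grade 1, that is 1.5 × 10^9/L or more on the table's bands, or baseline) is generally stricter than a corrected limit of 1.0.

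**The case against.** The strongest reply is that this is a one-word slip which any haematologist would read as per µL, and that the protocol protects patients by other routes. Table 2 holds drug for Grade 3 and 4 neutropenia, Section 6.1 holds drug and ends treatment after a long interruption, and Section 6.3 calls for a toxicity evaluation before each dose given in the clinic. The monotherapy data are also mild. Section 2.2.15 reports no Grade 4 events, and Section 7.3.2 places the related neutropenia at 360 mg with none of the events dose-limiting, whereas this trial gives 160 mg per dose.

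Most of that stands, and it rules out two stronger readings that a reader might infer. One is that the protocol lets any patient start a cycle with severe neutropenia. It does not: re-dosing a patient with drug-related Grade 3 or 4 neutropenia would breach Table 2. The other is that neutropenia could never delay cycle 2, so that dose-limiting toxicities would be undercounted. Section 5.1.4 does not tie the delay to the pre-cycle list, and Grade 4 neutropenia that fails to reach Grade 2 or lower within 7 days is dose-limiting in its own right.

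The reply does not rescue the criterion itself. A mandatory item is still wrong as printed, the attribution clause leaves a route around Table 2, and the reassuring data come from 15 myeloma patients, only 2 of them at 360 mg, on an intermittent schedule rather than 28 consecutive days.

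**Conclusion.** The pre-cycle ANC limit in Section 5.1.3 is wrong as written. It is a unit error in an operative safety threshold, a factor of 100,000 below the entry limit, and the criterion screens out essentially no neutropenic patient. That result is plain unit conversion and needs no outside assumption. That per µL was intended is an inference, though a strong one, from the exact match with both entry limits.

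Severity is low. The practical exposure is mainly neutropenia judged unrelated to study drug, plus conflicting instructions on Day 1 of a cycle. The documents give no basis for estimating how many patients that would involve. Response analysis, sample size, type I error and power do not change.

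One related discrepancy is not caused by the unit. With per µL restored, a patient recovering from Grade 3 to an ANC of 1.2 × 10^9/L would pass the pre-cycle check and satisfy Section 6.1, while Table 2 would still hold drug unless 1.2 is that patient's baseline.

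**What to change.** In Section 5.1.3 (Required Blood Parameters), restate the neutrophil limit as ANC ≥ 1.0 × 10^9/L (1000/µL), or another value the sponsor confirms, in the unit used in Section 3.1 and Table 2. Give the platelet limit its unit: ≥ 50 × 10^9/L. In the same edit, say whether the pre-cycle limit applies regardless of attribution, and which recovery level governs when Section 5.1.3, Section 6.1 and Table 2 differ. Any pre-cycle checklist or case report form that copied the per-dL figure should be corrected to match.

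The unit correction is two lines of protocol text, and the alignment adds a sentence or two. No further assessments, patients or analyses are needed.

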3.2 Exclusion Criteria

1. Prior Therapy
 - a. Patients who have had chemotherapy or radiotherapy within 2 weeks of study drug treatment or those who have not recovered from adverse events due to agents administered
 - b. No monoclonal antibody within 3 months unless evidence of disease progression.
2. Patients may not be receiving any other investigational agents.
3. Patients with known central nervous system metastases, including lymphomatous meningitis
4. Any known cardiac abnormalities such as:
 - Congenital long QT syndrome
 - QTc interval \geq 500 milliseconds;
5. Uncontrolled inter-current illness
6. Pregnant or nursing women
7. Patient is known to be Human Immunodeficiency Virus (HIV)-positive
8. Active Hepatitis A, Hepatitis B, or Hepatitis C infection
8. Patient has a history of surgery that would interfere with the administration or absorption of the oral study drugs

